### Model Specification to Predict Outcomes With Dosage

Construct by Outcome	Dependent Variables (follow-up)	Response Codes for Dependent Variables	Dependent Variable Type	Independent Variables
Primary outcome:				
Partner Relationship Behavior: 6 scaled items	DISAG_BE_FU	1 = none of the time to 5 = all of the time	Continuous	Dosage of curriculum; co-variates (using pre-survey scores)
5 scaled items	REL_BE_FU	1 = I am extremely good at this to 4 = I am extremely bad at this		
Secondary outcomes:				
Partner Relationship Attitudes: 9 scaled items	PARTREL_ATT_FU	1 = strongly agree to 4 = strongly disagree	Continuous	Dosage of curriculum; co-variates (using pre-survey scores)
3 scaled items	PARTREL_FUT_ATT_FU	1 = almost no chance to 5 = almost certain		
Sexual Attitudes: 7 scaled items	SEX_ATT_FU	1 = strongly agree to 4 = strongly disagree		
Financial Attitudes: 4 scaled items	FIN_ATT_FU	1 = strongly disagree to 7 = strongly agree		
Employment Attitudes 4 scaled items	EMP_ATT_FU	1 = strongly disagree to 7 = strongly agree		

Step 4 – run the linear regression model: Procedures to run the linear regression model are influenced by dependent variable types. Standard regression is necessary to model the influence of curriculum dosage on continuous dependent variables, such as when participants respond to

---

multiple items in a scaled construct by indicating levels of agreement with statements about key partner relationship attitudes.

Step 5 – interpret model results: Model results demonstrate the benefits of A-HBF participation whenever dosage variables predict more positive primary and secondary outcomes for a construct. For primary outcomes, benefits of receiving *SSHf* curriculum confirm hypotheses when respondents with higher levels of participation more frequently report ( $p < .05$ ):

1. Healthy partner relationship behavior

For secondary outcomes, benefits of receiving *SSHf* curriculum confirm hypotheses when respondents with higher levels of participation more frequently report ( $p < .05$ ):

2. More positive attitudes about partner relationships
3. More positive attitudes about sexual relationships
4. More positive attitudes about financial readiness
5. More positive attitudes about job readiness

---

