Research questions in this study are framed by a descriptive evaluation design to assess whether outcomes improve for at-risk and homeless youth after participating in the AVANCE-Houston Building Futures (A-HBF) Project. Primary outcomes will indicate whether behavior is improving over time for healthy relationships. Secondary benefits will indicate whether the attitudes that facilitate and reflect behavior for healthy family relationships and economic stability (financial and employment) are improving over time. Research questions that focus on primary and secondary outcomes for this study are presented below in Table 2.

Table 2: Outcome Research Questions

No	Research Question	Primary or Secondary Outcome?
R1	Do A-HBF participants report significantly healthier partner relationship attitudes after completing the SSHF curriculum in either a standard (weekly) or compressed (weekend retreat) workshop format and support services?	Secondary Outcome
R2	Do A-HBF participants report significantly healthier sexual attitudes after completing the SSHF curriculum in either a standard (weekly) or compressed (weekend retreat) workshop format and support services?	Secondary Outcome
R3	Do A-HBF participants report significantly healthier partner relationship behavior after completing the SSHF curriculum in either a standard (weekly) or compressed (weekend retreat) workshop format and support services?	Primary Outcome
R4	Do A-HBF participants report significantly healthier financial attitudes after completing the SSHF curriculum in either a standard (weekly) or compressed (weekend retreat) workshop format and support services?	Secondary Outcome
R5	Do A-HBF participants report significantly healthier employment attitudes after completing the SSHF curriculum in either a standard	Secondary Outcome

(weekly) or compressed (weekend retreat) workshop format and support services?

C. Relation to program logic model

Figure 1 in Appendix A presents a logic model to specify a theory of change for delivering A-HBF services. Service delivery processes specified in the model are linked to the desired outcomes for healthy relationships and economic readiness. Model specification incorporates a descriptive study design to conceptualize service delivery and the outcomes assessed for the A-HBF Project.

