These power analyses assume an Alpha Level of 0.05 with a two-tailed test and power level set at 0.80 (1 – Beta). The estimated effect sizes are all small effects or nearly small effects that would be detected, based on best practices outlined by Cohen (1988) of small effect sizes <0.02 and medium effect sizes <0.15. With these analyses, the proposed research design is demonstrated to measure large, medium, and small changes in participants' responses.

Table 4: Methods to Promote Sufficient Program Participation

What methods will you use to ensure sufficient sample is recruited, enrolls, and participates in the program?	AVANCE will work with schools and their community partners to recruit program participants, and AVANCE will provide incentives for program retention and completion. The CQI process will address issues regarding program recruitment and enrollment to ensure targets are met.
Who will be responsible for recruiting the evaluation sample?	The evaluation sample will not differ from the program population, in that all participants will be invited to participate in the evaluation. Enrollment into the evaluation will be conducted by the CQI Data Manager who will conduct the informed consent process and proctor the baseline data collection efforts.

Please describe any incentives to be offered for program participation and/or completion and/or data collection and/or participation in the evaluation.

Program Participation – AVANCE will provide a series of incentives for program retention (promotional items) and completion (\$75 gift card).

Evaluation Participation – No incentives will be used for the first two data collections- baseline and post-test, while participants are beginning or still engaged in services. A \$50 incentive will be used for the 1-year follow-up survey and will be provided in the form of a Walmart gift card.

D. Lead staff

See Appendix B for CVs of lead evaluation staff.

Table 5: Lead Evaluation Staff

Name	Organization	Role in the Evaluation
[name]	Midwest Evaluation and Research	Principal Investigator
[name]	Midwest Evaluation and Research	Lead Evaluation Consultant
[name], MA	Midwest Evaluation and Research	Evaluation Project Manager
[name]	Midwest Evaluation and Research	CQI Data Manager

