Partner Relationship Attitudes	9 items: levels of agreement with relationship beliefs (categories, 4-point); 3 items: likelihood of key relationship beliefs (categories, 5-point scale)	nFORM Healthy Marriage Youth Program Survey (A1.a-i; A2.a-c)	nFORM
Sexual Attitudes	7 items: levels of agreement with key sexual attitudes (categories, 4-point scale)	nFORM Healthy Marriage Youth Program Survey (B1.a-g)	nFORM
Partner Relationship Behavior	5 items: levels of reported skill with key relationship behaviors (categories, 4-point scale); 6 items: frequency engage in key relationship behaviors (categories, 5-point scale)	nFORM Healthy Marriage Youth Program Survey (C1b.a-e; C3.a-f)	nFORM
Financial Attitudes	4 items: levels of agreement with key financial	OLLE (Online Local	In appendix D of: Jurkiewicz, T. & Friedman, L. (2020). Impact Evaluation of The TYRO

	attitudes (categories, 7-point scale)	Evaluation) Survey	Champion Dads Project in Dallas, Texas: Final Impact Evaluation Report for Anthem Strong Families. Midwest Evaluation and Research.
Employment Attitudes	4 items: levels of agreement with key employment attitudes (categories, 7-point scale)	OLLE (Online Local Evaluation) Survey	In appendix D of: Jurkiewicz, T. & Friedman, L. (2020). Impact Evaluation of The TYRO Champion Dads Project in Dallas, Texas: Final Impact Evaluation Report for Anthem Strong Families. Midwest Evaluation and Research.

Consent:

Because the planned evaluation involves human subjects, AVANCE understands program implementation requires both IRB approval and participant informed consent. MER has an established relationship with Solutions IRB, having secured more than 14 IRB approvals and renewals for evaluations it has conducted during the past four years. IRB clearance will be submitted for approval and obtained during the planning period.

Each school location will have a signed letter of agreement to be included in this project. This must be filed with the IRB during the application process. Any school locations that are later recruited into the study will result in MER submitting amendments to the IRB to include these schools as research sites, and the additional school's letter will be included in the project.

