## IV. Data Analysis

### A. Data analysis

To examine the research questions, a repeated measures design will be used. The within-subjects factor will be the time of measurement (pre-survey and 12-month follow-up survey), and the between-subjects factor will be the format of the SSHF curriculum (standard or compressed) and support services.

Descriptive statistics will be computed to summarize the demographic variables and the variables of interest. Shapiro-Wilk tests will be conducted to assess the normality of the data. If the data are not normally distributed, appropriate transformations will be applied, or nonparametric tests will be used. To examine the first research question, a repeated measures analysis of variance (ANOVA) will be conducted with partner relationship attitudes as the dependent variable. The between-subjects factor will be the format of the SSHF curriculum, and the within-subjects factor will be time of measurement. If significant main effects or interactions are found, post hoc tests (e.g., Bonferroni) will be conducted to examine the pairwise comparisons.

The same approach will be used for the remaining research questions, with sexual attitudes, partner relationship behavior, financial attitudes, and employment attitudes as dependent variables. The level of statistical significance will be set at  $p < 0.05$ . Effect sizes will be reported using partial eta-squared ( $\eta^2$ ), which provides an estimate of the proportion of variance in the dependent variable accounted for by each factor in the ANOVA.

To examine the reliability of the scales, Cronbach's alpha will be computed for each construct. A value of 0.70 or higher will indicate acceptable reliability. To examine the validity of the scales, confirmatory factor analysis (CFA) will be conducted to test the hypothesized factor structure of each construct. If the hypothesized factor structure does not fit the data well, exploratory factor analysis (EFA) will be conducted to identify the underlying factor structure. Missing data will be handled using multiple imputation techniques to minimize bias and increase power. Overall, this study will use a repeated measures design with ANOVA to examine the effects of the SSHF curriculum on various domains of relationship and personal functioning and will use reliability and validity analyses to ensure the psychometric properties of the measures.

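### The sole primary outcome is one dependent variable in the SAP text but two scales in its model table, with no stated rule for scoring, combining or testing them

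*SAP*

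**What the plan says.** Protocol I.B, Table 2, marks one research question as primary, R3, which opens "Do A-HBF participants report significantly healthier partner relationship behavior after completing the" SSHF curriculum. SAP IV.A describes a repeated-measures ANOVA for the first question and repeats it "with sexual attitudes, partner relationship behavior, financial attitudes, and employment attitudes as dependent variables". The dosage regression in the same section also lists partner relationship behavior once.

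The SAP table headed Model Specification to Predict Outcomes With Dosage puts two follow-up variables under that construct:

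- DISAG_BE_FU: six items, coded "1 = none of the time to 5 = all of the time".
- REL_BE_FU: five items, coded "1 = I am extremely good at this to 4 = I am extremely bad at this".

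Protocol III.A, Table 6, has the same two item blocks under one construct. The first is described only as "6 items: frequency engage in key relationship behaviors (categories, 5-point scale", and the item wording is not given.

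On error control, SAP IV.A states "The level of statistical significance will be set at" p < 0.05. Bonferroni appears only as an example for pairwise comparisons after a significant ANOVA. Step 5 says benefit is shown whenever dosage predicts more positive outcomes for a construct, and attaches p < .05 to the primary construct as a whole. Protocol I.D calls the hypotheses for all five constructs confirmatory.

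**The concern.** An analyst holding both documents cannot tell which number answers R3. Three readings are open: one score from all eleven items, two scales that must both succeed, or two scales of which either is enough. The documents choose none of them, and the readings have different error rates. Under the either-scale reading, the only primary claim gets two unadjusted chances at 0.05.

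Direction is also unsettled. REL_BE_FU is coded so that benefit is a negative dosage coefficient, while Step 5 speaks of more positive outcomes. The direction of DISAG_BE_FU depends on whether its items describe healthy or unhealthy conduct. If these choices are made after follow-up data are seen, the primary result depends on them.

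**Working it through.** **1. Passages side by side.** Table 2 of the protocol and the SAP IV.A text have one primary outcome and one dependent variable. The SAP model table has two dependent variables with different item counts (6 and 5), ranges (1–5 and 1–4) and response codes. The available text has no composite formula, reversal rule or either/both rule.

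**2. The plan's own figures.** Protocol II.C says "These power analyses assume an Alpha Level of 0.05 with a two-tailed test and power level set at 0.80", with detectable effects of 0.017 at N = 1105 and 0.023 at N = 774. The follow-up N agrees with 0.70 × 1105 = 773.5. I used a noncentral F for linear regression with λ = f²·N and degrees of freedom u and N − u − 1. The number of predictors u is not stated. Reproducing 0.017 needs u = 14 or 15 (0.0168, 0.0172), and 0.023 needs u = 12 or 13 (0.0227, 0.0234). At u = 13 the stated effects have power of about 0.82 and 0.79. The figures are therefore plausible, but only on an assumed u. What matters here is that they use an undivided alpha of 0.05.

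**3. Either scale sufficient.** With two independent two-sided tests at 0.05:

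1 − (1 − 0.05)² = 1 − 0.9025 = 0.0975.

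Counting only false findings of benefit (0.025 per test):

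1 − (1 − 0.025)² = 1 − 0.950625 = 0.0494.

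For correlated tests I used the bivariate normal probability that at least one rejects. The correlation is not in the documents, so a range is shown:

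| Correlation of the two tests | Either rejects, two-sided 0.05 each | Benefit direction only | Two-sided 0.025 each |
|---|---|---|---|
| 0 | 9.75% | 4.9% | 4.9% |
| 0.3 | 9.5% | 4.8% | 4.8% |
| 0.5 | 9.1% | 4.5% | 4.7% |
| 0.7 | 8.4% | 4.2% | 4.3% |
| 0.9 | 7.0% | 3.5% | 3.6% |

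The last column is Bonferroni. When neither scale has an effect, Holm gives the same rate, because its first step is at 0.025.

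**4. Both scales required.** A false claim needs a false rejection on at least one scale and a rejection on the other. Its probability cannot exceed the 5% of a single test, so there is no inflation.

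**5. One composite.** The effect depends on the unknown keying of DISAG_BE_FU:

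- Healthy items: the two scales run in opposite directions, and an unreversed sum loses part of the effect.
- Unhealthy items: both scales run the same way and nothing cancels, but a higher score means worse behavior.
- Mixed items: DISAG_BE_FU partly cancels within itself.

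To illustrate the first case only, assume equal standardized improvement on both scales and item SDs s₁ (frequency) and s₂ (skill). The share of the raw change kept by an unreversed eleven-item sum is (6s₁ − 5s₂)/(6s₁ + 5s₂). Equal SDs give 1/11 = 9%. Assumed SDs of 1.0 and 0.75 give 2.25/9.75 = 23%. The SDs are not in the documents.

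**The case against.** The strongest reply is that the construct name in the text and the variable names in the table are shorthand for one plan: two separately named scales, analysed separately. Step 5 sets its threshold for the construct and never says that either scale suffices, so two unadjusted chances at the primary claim are an inference. Step 5 also defines benefit in words, so an analyst who knows the codes can read a negative REL_BE_FU coefficient correctly. The planned Cronbach's alpha and confirmatory factor analysis would probably expose an unreversed block. Steps 4 and 5 appear without Steps 1 to 3 in the available text, so a scoring step elsewhere cannot be excluded. The evaluation is also a single-group, descriptive one.

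Much of this limits the point. A reader might infer more than the documents support:

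- That the two scales are coded in opposite directions. Only the REL_BE_FU direction is shown.
- That a composite would lose 77% of the effect (keeping 23%). This needs a raw eleven-item score that no section plans, no reversal, healthy keying and assumed SDs.
- That the chance of success doubles. What can rise is the false-positive chance, and 9.75% is its ceiling.
- That primary error reaches 30%. That is 1 − 0.95⁷ = 30.2% over all seven table variables, which mixes primary and secondary outcomes.

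What the reply does not supply is a rule. Separate analysis of two scales still needs an either/both statement. The reliability and factor checks come after the data are seen, and the exploratory factor analysis fallback adds a data-driven choice of scale.

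**Conclusion.** The point holds in a limited form. The sole primary outcome is not uniquely defined: its composition, its direction and its decision rule are all unstated in the available text, and no error control covers its two scales. If either scale can carry the claim, the primary false-positive chance rises from 5% to between 7.0% (correlation 0.9) and 9.75% (independent). In the benefit direction it rises from 2.5% to between 3.5% and 4.9%. These figures assume a non-negative correlation once both scales are aligned, and count only the two scales within one model. Under a both-scales rule the inflation is zero. Loss of effect in a composite is a conditional risk and not a shown defect: it needs healthy or mixed keying of DISAG_BE_FU and no reversal.

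**What to change.** Before follow-up data are analysed, amend the SAP to:

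- State the direction of every item and key all items so that higher is healthier. REL_BE_FU must be reversed. DISAG_BE_FU must be checked item by item.
- Define the primary outcome in one of two ways: (a) name one scale as the single primary outcome, or (b) keep both and state the rule. If success on either suffices, use Holm (0.025 for the smaller p-value, then 0.05). If both must succeed, test each at 0.05. Avoid the bare term co-primary, which does not say which rule is meant.
- Use the same definition in the repeated-measures ANOVA and the dosage regression.
- Treat the four secondary constructs as supportive, and state scoring and direction there too. Partner relationship attitudes is also split into two variables.

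Options (a) and both-must-succeed need wording only, although the second is harder to pass. The either-scale rule has a slightly stricter first threshold. For a single tested coefficient at power 0.80, by the same noncentral F method with u = 1, the detectable f² moves from 0.0102 to 0.0123 at N = 774 and from 0.0071 to 0.0086 at N = 1105. No new data are needed.

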Desired Outcomes: Outcomes specified in the logic model theorize the primary and secondary outcomes that are desired for participants after they complete A-HBF services. Secondary outcomes are the improved attitudes that indicate and reflect participant engagement in healthy partner relationship behaviors and capacity for future economic stability. Primary outcomes are the healthier behaviors exhibited by participants for partner relationships that ultimately define the participation benefits for the A-HBF Project. All outcomes specified in the logic model are theorized to be more positive for eligible at-risk and homeless youth after they complete primary services and support services.

D. Hypotheses

Table 3 below presents the hypotheses associated with the primary and secondary research questions for this descriptive study. Primary and secondary outcomes are reported on participant survey measures that are administered shortly after A-HBF enrollment and again one year later after study groups complete services (or should have completed them). Confirmatory hypotheses focus on the extent to which participants report improved attitudes (partner relationship, sexual, financial, and employment) and behaviors (partner relationship) after A-HBF participation.

Table 3: Hypothesized Results

Research Question	Hypothesized Result
R1	Participants will report healthier partner relationship attitudes after they complete primary services and support services in the A-HBF Project.
R2	Participants will report healthier sexual attitudes after they complete primary services and support services in the A-HBF Project.
R3	Participants will report healthier partner relationship behavior after they complete primary services and support services in the A-HBF Project.
R4	Participants will report healthier financial attitudes after they complete primary services and support services in the A-HBF Project.
R5	Participants will report healthier employment attitudes after they complete primary services and support services in the A-HBF Project.

II. Research Design and Staff

A. Research design

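### The only stated confirmation rule (SAP Step 5) rests on a dosage slope, which does not test the hypothesised improvement over time in R1-R5

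*SAP*

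**What the plan says.** **The hypotheses.** Protocol section I.D states: "Confirmatory hypotheses focus on the extent to which participants report improved attitudes (partner relationship, sexual, financial, and employment) and behaviors". Table 3 words the primary one, R3, as: "Participants will report healthier partner relationship behavior after they complete primary services and support services in the A-HBF Project". R1, R2, R4 and R5 are worded alike. All five concern change from before to after.

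**The analysis of the research questions.** SAP section IV.A opens: "To examine the research questions, a repeated measures design will be used". It continues: "The within-subjects factor will be the time of measurement (pre-survey and 12-month follow-up survey", with curriculum format as the between-subjects factor. The first question is described in full, and then "The same approach will be used for the remaining research questions". The threshold is p < 0.05. This text examines the questions but does not say when a hypothesis counts as confirmed.

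**The dosage model.** SAP section IV.A then adds a regression of pre-to-post change on hours attended, controlling for format, support services and related demographics. The table under Model Specification to Predict Outcomes With Dosage differs: the dependent variables are follow-up scores, and the predictors are dosage and covariates using pre-survey scores. Step 5 gives the decision rule: "Model results demonstrate the benefits of A-HBF participation whenever dosage variables predict more positive primary and secondary outcomes for a construct". It goes on to treat the hypotheses for the same five constructs as confirmed when respondents with higher participation report better outcomes at p < .05.

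**A third description.** The power analysis in protocol section II.C says that a linear regression on participant characteristics will address the primary and secondary questions.

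**The design.** Protocol section I.B states: "Research questions in this study are framed by a descriptive evaluation design". There is one group, and section II.B declares the development of study groups not relevant.

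**The concern.** The rule that announces success does not test the statement it is said to confirm. Table 3 asks whether participants got better. Step 5 asks whether those who attended more hours scored better than those who attended fewer. These are different quantities and can point in opposite directions.

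Hours are also not assigned. Whatever leads a young person to attend more may lead to better scores a year later, and adjustment for the pre-survey score removes only baseline differences. Part of the variation in hours comes from format, which the table under Model Specification does not list as a covariate.

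At stake is the primary conclusion. The report could state that benefits were demonstrated when average scores did not move or fell. It could also fail to confirm a hypothesis that the time effect clearly supports. No text ranks the analyses or says what to conclude if they disagree.

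**Working it through.** **1. The plan's own figures.** Protocol section II.C gives minimum detectable effects of 0.017 (N=1105, post-test) and 0.023 (N=774, follow-up), at two-sided alpha 0.05 and power 0.80. The benchmarks cited there (0.02 and 0.15) suggest Cohen's f². The number of predictors is not stated, so the figures cannot be reproduced from the stated inputs alone. Solving the noncentral F with λ = f²N, 13 predictors give 0.0163 and 0.0234, and 14 give 0.0168 and 0.0241. The figures are therefore plausible for a joint test of about 13 to 14 predictors. They describe neither test discussed here:
- A one-degree-of-freedom dosage slope has detectable f² of 0.0071 (N=1105) and 0.0102 (N=774).
- A mean change has detectable d_z = (1.96 + 0.84)/√774 = 2.80/27.82 = 0.101.

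**2. The slope is blind to average change (no assumptions needed).** With D the dosage after removing covariates, the slope is b = Cov(D, Y)/Var(D). Replace Y by Y + c for everyone: Cov(D, Y + c) = Cov(D, Y), so b and its p-value do not move. Two cases follow:
- Half the sample attends more and stays the same; the other half attends less and declines by δ. Mean change is −δ/2 and nobody improved, yet the slope is positive and Step 5 can confirm.
- Everyone improves by δ whatever their hours. The slope is zero, so Step 5 confirms only by chance (about 2.5% in the favourable direction).

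**3. Illustrative size of false confirmation.** N = 774 applies because every dependent variable in the table under Model Specification is a follow-up score. The correlations are assumed and must be those left after covariate adjustment. With no programme effect, the spurious dose-outcome correlation r is the product of the trait's two correlations, and

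P(positive and two-sided p < 0.05) = Φ(atanh(r)·√(774 − 3) − 1.96), with √771 = 27.77.

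| Trait-dosage | Trait-outcome | r | atanh(r)·27.77 | Probability |
|---|---|---|---|---|
| 0.2 | 0.2 | 0.04 | 1.11 | Φ(−0.85) = 20% |
| 0.3 | 0.2 | 0.06 | 1.67 | Φ(−0.29) = 39% |
| 0.4 | 0.25 | 0.10 | 2.79 | Φ(0.83) = 80% |

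**4. Both analyses on the same simulated data.** N = 774, no effect of dosage, SD 1. Assumed: pre/follow-up correlation 0.5, and a trait correlated 0.3 with attendance that shifts the follow-up score by 0.2 SD per SD of trait.
- True mean change zero: the time effect shows improvement in 2-3% of runs; Step 5 confirms in 47%.
- Average 0.2 SD worse: the time effect shows worsening in essentially all runs; Step 5 still confirms in 50%.
- Average 0.2 SD better, with no trait effect: the time effect detects it in essentially all runs; Step 5 confirms in about 2%.

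The rates near 50% exceed the 39% in the table because the trait effect is set here before adjustment. Removing the variance explained by the pre-survey score raises the remaining correlation.

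**5. Availability of the deciding contrast.** Protocol Table 6 places the measures for R1-R3 in the nFORM survey. Table 8 lists nFORM and OLLE at baseline and post-test, but only OLLE at one year. As written, the 12-month scores for R1-R3, including the primary outcome, are not shown to be collected.

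**The case against.** The strongest defence is that the ANOVA already answers the research questions and the dosage regression merely adds to it. The order of the SAP text supports this in part, and both analyses can properly be reported. It fails on Step 5, which covers the labelled primary outcome, uses the language of confirmation and is nowhere marked supplementary.

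Other points on that side stand:
- A reader might infer that the plan lets success be claimed from whichever analysis is significant. No text says so. The ANOVA section states a threshold but no confirmation rule. What is documented is one explicit rule that tests the wrong quantity, and no ranking.
- A reader might count two primary scales times two analyses as four chances at 0.05, giving 1 − 0.95⁴ = 18.5%. That counts unfavourable results too. Favourable results alone give 1 − 0.975⁴ = 9.6%, and only if the tests are independent, which is unlikely in the same youth. The split into two scales also appears only in the dosage table. I do not rely on either figure.
- A reader might apply N=1105 to Step 5. That is the post-test count and does not fit follow-up outcomes.
- Calling attendance self-selected is an inference. The documents show that hours are not assigned and depend partly on format (14 hours against 16 + 2 = 18). They do not say what else drives them.
- Expected completion is 90%, so hours may vary little within format.
- The lack of a comparison group is openly declared. What remains is causal wording in the SAP that goes beyond a descriptive design.

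**Conclusion.** The point holds and should be fixed before analysis. The only explicit confirmation rule does not test the hypotheses in Table 3. That follows from the algebra of the slope and needs no assumption.

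The size of the risk is illustrative. With assumed correlations after adjustment, N=774 and no programme effect, Step 5 confirms in 20% to 80% of studies, and in 39% for the middle case. The true rate cannot be derived from the documents. If the time contrast decides instead, the chance of declaring improvement when true mean change is zero is about 2.5% per outcome, whatever drives attendance.

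Even a significant time effect would show change and not a programme effect, because there is no comparison group.

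**What to change.** 1. In SAP section IV.A, state that each of R1-R5 is decided only by the baseline-to-12-month time contrast, in the healthier direction. Twelve months is already the plan's timepoint in protocol section I.D and SAP section IV.A. Define the healthier direction for each scale: the five-item skill scale, for example, is coded from good (1) to bad (4).
2. In Step 5, remove the statements that benefits are demonstrated and hypotheses confirmed. Label the dosage model exploratory and associational, and adjust it for format.
3. Rewrite the power and analysis text in protocol section II.C to match the deciding test, and give its detectable effect.
4. In SAP section IV.A, replace the language of effects and impact with change and association.
5. Reconcile protocol Table 8 with Table 6, so that the R1-R3 items are shown to be collected at one year.

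The cost is wording in both documents, a more modest conclusion, and confirmation that the R1-R3 items are collected at 12 months. If they are not, the contrast cannot be computed for the primary outcome, and that must be settled first.
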